7.1.1.2 Inclusion/Exclusion Criteria

All inclusion and exclusion criteria will be reviewed by the investigator or qualified designee to ensure that the subject qualifies for the trial.

7.1.1.3 Medical History

A medical history will be obtained by the investigator or qualified designee. Medical history will include all active conditions, and any condition diagnosed within the prior 10 years that are considered to be clinically significant by the Investigator. Details regarding the disease for which the subject has enrolled in this study will be recorded separately and not listed as medical history.

7.1.1.4 Prior and Concomitant Medications Review

7.1.1.4.1 Prior Medications

The investigator or qualified designee will review prior medication use, including any protocol-specified washout requirement, and record prior medication taken by the subject within 28 days before starting the trial. Treatment for the disease for which the subject has enrolled in this study will be recorded separately and not listed as a prior medication.

7.1.1.4.2 Concomitant Medications

The investigator or qualified designee will record medication, if any, taken by the subject during the trial. All medications related to reportable SAEs and ECIs should be recorded as defined in Section 7.2.

7.1.1.5 Disease Details and Treatments

7.1.1.5.1 Disease Details

The investigator or qualified designee will obtain prior and current details regarding disease status.

7.1.1.5.2 Prior Treatment Details

The investigator or qualified designee will review all prior cancer treatments including systemic treatments, radiation and surgeries.

7.1.1.5.3 Subsequent Anti-Cancer Therapy Status

The investigator or qualified designee will review all new anti-neoplastic therapy initiated after the last dose of trial treatment. If a subject initiates a new anti-cancer therapy within 30 days after the last dose of trial treatment, the 30-day Safety Follow-up visit must occur before

the first dose of the new therapy. Once new anti-cancer therapy has been initiated the subject will move into survival follow-up.

7.1.1.6 Assignment of Screening Number

The Sponsor-Investigator will assign each patient a de-identified screening number that will be used for data tracking purposes.

7.1.2 Clinical Procedures/Assessments

7.1.2.1 Adverse Event (AE) Monitoring

The investigator or qualified designee will assess each subject to evaluate for potential new or worsening AEs as specified in the Trial Flow Chart and more frequently if clinically indicated. Adverse experiences will be graded and recorded throughout the study and during the follow-up period according to NCI CTCAE Version 4.0 (see Section 11.2). Toxicities will be characterized in terms regarding seriousness, causality, toxicity grading, and action taken with regard to trial treatment.

For subjects receiving treatment with pembrolizumab all AEs of unknown etiology associated with pembrolizumab exposure should be evaluated to determine if it is possibly an event of clinical interest (ECI) of a potentially immunologic etiology (termed immune-related adverse events, or irAEs); see the separate ECI guidance document in Appendix 4 regarding the identification, evaluation and management of potential irAEs.

Please refer to section 7.2 for detailed information regarding the assessment and recording of AEs.

7.1.2.2 Full Physical Exam

The investigator or qualified designee will perform a complete physical exam during the screening period. Clinically significant abnormal findings should be recorded as medical history. A full physical exam should be performed during screening.

7.1.2.3 Directed Physical Exam

For cycles that do not require a full physical exam per the Trial Flow Chart, the investigator or qualified designee will perform a directed physical exam as clinically indicated prior to trial treatment administration.

7.1.2.4 Vital Signs

Vital signs will be taken at screening, prior to the administration of each dose of trial treatment and at treatment discontinuation as specified in the Trial Flow Chart (Section 6.0). Vital signs should include temperature, pulse, respiratory rate, weight and blood pressure. Height will be measured at screening only.

7.1.2.5 Eastern Cooperative Oncology Group (ECOG) Performance Scale

The investigator or qualified designee will assess ECOG status (see Section 10.4) at screening, prior to the administration of each dose of trial treatment and discontinuation of trial treatment as specified in the Trial Flow Chart.

7.1.2.6 Tumor Imaging and Assessment of Disease

Radiology at the Seattle Cancer Care Alliance will perform RECIST. Patients will have a CT of the chest, abdomen and pelvis at each imaging visit. Patients whose RECIST evaluable disease is only outside the chest abdomen and pelvis (e.g. neck or extremities) must also have this disease imaging. For patients who have RECIST evaluable disease in their chest/ abdomen/ pelvis as well as outside this area, additional imaging may be performed as deemed appropriate or necessary by their treating clinician.

7.1.2.7 Tumor Tissue Collection and Correlative Studies Blood Sampling

At the time of enrollment, all patients will have 12 slides (5 microns of tissue on a baked, charged slide) cut. These will be kept at 2-8 degrees Celsius until they are ready to be either to QualTek for PD-L1 IHC or Merck Research Laboratories. Other biomarkers such as PD-1 expression, as well as potentially IHC for immune infiltrates and assessment of immune response related genes using an N-counter Nanostring assay. Additional archived tissue may also be requested for multiplex immunohistochemistry and gene expression assays. At time points specified in **section 6.1**, 30 mL PBMC and 10 mL serum will be frozen and delivered to the [name] Laboratory at the Fred Hutchinson Cancer Research Center for flow cytometry and functional analysis.

7.1.3 Laboratory Procedures/Assessments

Details regarding specific laboratory procedures/assessments to be performed in this trial are provided below.

Laboratory tests for hematology, chemistry, urinalysis, and others are specified in Table 5.

Table 5 Laboratory Tests

Hematology	Chemistry	Urinalysis	Other
Hematocrit	Albumin	Blood	Serum β -human chorionic gonadotropin†
Hemoglobin	Alkaline phosphatase	Glucose	(β -hCG)†
Platelet count	Alanine aminotransferase (ALT)	Protein	PT (INR)
WBC (total and differential)	Aspartate aminotransferase (AST)	Specific gravity	aPTT
Red Blood Cell Count	Lactate dehydrogenase (LDH)	Microscopic exam (If abnormal)	Total triiodothyronine (T3)
Absolute Neutrophil Count	Carbon Dioxide ‡	results are noted	Free tyroxine (T4)
Absolute Lymphocyte Count	(CO₂ or biocarbonate)	Urine pregnancy test †	Thyroid stimulating hormone (TSH)
	Uric Acid		PK
	Calcium		
	Chloride		Blood for correlative studies
	Glucose		
	Phosphorus		
	Potassium		
	Sodium		
	Magnesium		
	Total Bilirubin		
	Direct Bilirubin (If total bilirubin is elevated above the upper limit of normal)		
	Total protein		

Hematology	Chemistry	Urinalysis	Other
	Blood Urea Nitrogen		
† Perform on women of childbearing potential only. If urine pregnancy results cannot be confirmed as negative, a serum pregnancy test will be required. ‡ If considered standard of care in your region.			

Laboratory tests for screening should be performed within 14 days prior to the first dose of treatment. If within 3 days of Cycle 1 Day 1, the screening lab results may be utilized for Cycle 1 Day 1. After Cycle 1, pre-dose laboratory procedures can be conducted up to 72 hours prior to dosing. Results must be reviewed by the investigator or qualified designee and found to be acceptable prior to each dose of trial treatment.

7.1.3.1 Pharmacokinetic/Pharmacodynamic Evaluations

7.1.3.1.1 Blood Collection for Serum Pembrolizumab

Given the prior extremely consistent pharmacokinetics of Pembrolizumab, no pharmacokinetic analysis will be performed in this study.

7.1.3.1.2 Anti-Pembrolizumab Antibodies

Given the lack of anti-pembrolizumab antibodies seen in prior trials, no assessment will be made for these in this study.

7.1.4 Other Procedures

7.1.4.1 Withdrawal/Discontinuation

When a subject discontinues/withdraws prior to trial completion, all applicable activities scheduled for the final trial visit should be performed at the time of discontinuation. Any adverse events, which are present at the time of discontinuation/withdrawal, should be followed in accordance with the safety requirements outlined in Section 7.2 - Assessing and Recording Adverse Events. Subjects who a) attain a CR or b) complete 24 months of treatment with pembrolizumab may discontinue treatment with the option of restarting treatment if they meet the criteria specified in Section 7.1.5.5. After discontinuing treatment following assessment of CR, these subjects should return to the site for a Safety Follow-up Visit (described in Section 7.1.5.3.1) and then proceed to the Follow-Up Period of the study (described in Section 7.1.5.4).

A subject will be considered withdrawn and no longer followed if they enroll onto hospice care.

7.1.5 Visit Requirements

Visit requirements are outlined in Section 6.0 - Trial Flow Chart. Specific procedure-related details are provided above in Section 7.1 - Trial Procedures.

7.1.5.1 Screening

The Sponsor-Investigator or a qualified designee will ensure that all inclusion and exclusion criteria have been met. Patients who initially fail screening may retake any test and enroll once they meet eligibility.

7.1.5.1.1 Screening Period

Unless otherwise specified, all clinical assessments including lab work must be done within 14 days of treatment initiation. Screening lab work may be utilized for Cycle 1 Day 1 lab work if done within 3 days of treatment initiation. Radiological assessment can be done within 28 days prior to first dose of study medication. Echocardiogram or MUGA scan may have been done up to 3 months of starting on study.

7.1.5.2 Treatment Period

Patients must be evaluated by a sarcoma provider prior to each infusion. In general, these visits will be the day of the infusion but could be up to 72 hours prior so long as labs are adequate. Visits where scan results will be reviewed should include an oncologist.

7.1.5.3 Post-Treatment Visits

Patients will be seen at the time of discontinuation and then again 30 days later. These visits may be conducted by an oncologist or one of the APP's.

7.1.5.3.1 Safety Follow-Up Visit

The mandatory Safety Follow-Up Visit should be conducted approximately 30 days after the last dose of trial treatment or before the initiation of a new anti-cancer treatment, whichever comes first. All AEs that occur prior to the Safety Follow-Up Visit should be recorded. Subjects with an AE of Grade > 1 will be followed until the resolution of the AE to Grade 0-1 or until the beginning of a new anti-neoplastic therapy, whichever occurs first. SAEs that occur within 30 days of the end of treatment or before initiation of a new anti-cancer treatment, whichever is earlier, should also be followed and recorded. Subjects who are eligible for retreatment with pembrolizumab (as described in Section 7.1.5.5) may have up to two safety follow-up visits, one after the Treatment Period and one after the Second Course Phase.

If a patient goes onto hospice, then they will no longer be followed and considered withdrawn from the study.

7.1.5.3.1 Survival Follow-up

Once a subject experiences confirmed disease progression or starts a new anti-cancer therapy, the subject moves into the survival follow-up phase and should be contacted by telephone every 12 weeks to assess for survival status until death, withdrawal of consent, or the end of the study, whichever occurs first.

7.2 Assessing and Recording Adverse Events

An adverse event is defined as any untoward medical occurrence in a patient or clinical investigation subject administered a pharmaceutical product and which does not necessarily have to have a causal relationship with this treatment. An adverse event can therefore be any unfavorable and unintended sign (including an abnormal laboratory finding, for example), symptom, or disease temporally associated with the use of a medicinal product or protocol-specified procedure, whether or not considered related to the medicinal product or protocol-specified procedure. Any worsening (i.e., any clinically significant adverse change in frequency and/or intensity) of a preexisting condition that is temporally associated with the use of the Merck's product, is also an adverse event.

Changes resulting from normal growth and development that do not vary significantly in frequency or severity from expected levels are not to be considered adverse events. Examples of this may include, but are not limited to, teething, typical crying in infants and children and onset of menses or menopause occurring at a physiologically appropriate time.

Merck product includes any pharmaceutical product, biological product, device, diagnostic agent or protocol-specified procedure, whether investigational (including placebo or active comparator medication) or marketed, manufactured by, licensed by, provided by or distributed by Merck for human use.

Adverse events may occur during the course of the use of Merck product in clinical trials or within the follow-up period specified by the protocol, or prescribed in clinical practice, from overdose (whether accidental or intentional), from abuse and from withdrawal.

Adverse events may also occur in screened subjects during any pre-allocation baseline period as a result of a protocol-specified intervention, including washout or discontinuation of usual therapy, diet, placebo treatment or a procedure.

Progression of the cancer under study is not considered an adverse event unless it is considered to be drug related by the investigator.

All adverse events will be recorded from the time the consent form is signed through 30 days following cessation of treatment and at each examination on the Adverse Event case report forms/worksheets. The reporting timeframe for adverse events meeting any serious criteria is described in section 7.2.3.1.

7.2.1 Definition of an Overdose for This Protocol and Reporting of Overdose to the Sponsor-Investigator and to Merck

For purposes of this trial, an overdose of pembrolizumab will be defined as any dose of 1,000 mg or greater (\geq times the indicated dose). No specific information is available on the treatment of overdose of pembrolizumab. Appropriate supportive treatment should be provided if clinically indicated. In the event of overdose, the subject should be observed closely for signs of toxicity. Appropriate supportive treatment should be provided if clinically indicated.

If an adverse event(s) is associated with (“results from”) the overdose of a Merck product, the adverse event(s) is reported as a serious adverse event, even if no other seriousness criteria are met.

If a dose of Merck’s product meeting the protocol definition of overdose is taken without any associated clinical symptoms or abnormal laboratory results, the overdose is reported as a non-serious Event of Clinical Interest (ECI), using the terminology “accidental or intentional overdose without adverse effect.”

All reports of overdose with and without an adverse event must be reported within 24 hours to the Sponsor-Investigator and within 2 working days hours to Merck Global Safety. (Attn: Worldwide Product Safety; [contact])

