3.0 OBJECTIVES & HYPOTHESES

3.1 Primary Objectives & Hypotheses

3.1.1 Objective: To assess the safety and tolerability of the combination of Pembrolizumab and Doxorubicin in patients with advanced soft tissue sarcoma (STS).

Hypothesis: The combination of Doxorubicin and Pembrolizumab will be similar to the toxicity of standard Doxorubicin and Pembrolizumab therapy when these drugs are used as single agents.

3.1.2 Objective: To assess the clinical response rate of advanced soft tissue sarcoma (STS) patients receiving the combination of Pembrolizumab and Doxorubicin.

Hypothesis: The addition of Pembrolizumab to Doxorubicin will result in a 20% increase in the objective response rate (CR + PR) compared with historical controls.

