5.2.1.2 Dose Modification of Pembrolizumab

AEs associated with pembrolizumab exposure may represent an immunologic etiology. These immune-related AEs (irAEs) may occur shortly after the first dose or several months after the last dose of pembrolizumab treatment and may affect more than one body system simultaneously. Therefore, early recognition and initiation of treatment is critical to reduce complications. Based on existing clinical study data, most irAEs were reversible and could be managed with interruptions of pembrolizumab, administration of corticosteroids and/or other supportive care. For suspected irAEs, ensure adequate evaluation to confirm etiology or exclude other causes. Additional procedures or tests such as bronchoscopy, endoscopy, skin biopsy may be included as part of the evaluation. Based on the severity of irAEs, withhold or permanently discontinue pembrolizumab and administer corticosteroids. Dose modification and toxicity management guidelines for irAEs associated with pembrolizumab are provided in

Table

3.

Table 3 Dose modification and toxicity management guidelines for immune-related AEs associated with pembrolizumab

General instructions:				

 1. Corticosteroid taper should be initiated upon AE improving to Grade 1 or less and continue to taper over at least 4 weeks. 2. For situations where pembrolizumab has been withheld, pembrolizumab can be resumed after AE has been reduced to Grade 1 or 0 and corticosteroid has been tapered. Pembrolizumab should be permanently discontinued if AE does not resolve within 12 weeks of last dose or corticosteroids cannot be reduced to ≤ 10 mg prednisone or equivalent per day within 12 weeks. 3. For severe and life-threatening irAEs, IV corticosteroid should be initiated first followed by oral steroid. Other immunosuppressive treatment should be initiated if irAEs cannot be controlled by corticosteroids. 				
Immune-related AEs	Toxicity grade or conditions (CTCAEv4.0)	Action taken to pembrolizumab	irAE management with corticosteroid and/or other therapies	Monitor and follow-up

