7.2.3 Immediate Reporting of Adverse Events to the Sponsor-Investigator and to Merck

7.2.3.1 Serious Adverse Events

A serious adverse event is any adverse event occurring at any dose or during any use of Merck’s product that:

- Results in death;
- Is life threatening;
- Results in persistent or significant disability/incapacity;
- Results in or prolongs an existing inpatient hospitalization;
- Is a congenital anomaly/birth defect;
- Is a new cancer (that is not a condition of the study);

- Is associated with an overdose;
- Is another important medical event

Refer to Table 6 for additional details regarding each of the above criteria.

Any serious adverse event, or follow up to a serious adverse event, including death due to any cause other than progression of the cancer under study that occurs to any subject from the time the consent is signed through 30 days following cessation of treatment, or the initiation of new anti-cancer therapy, whichever is earlier, whether or not related to Merck product, must be reported within 24 hours to the Sponsor-Investigator and within 2 working days to Merck Global Safety.

Non-serious Events of Clinical Interest will be forwarded to Merck Global Safety and will be handled in the same manner as SAEs.

Additionally, any serious adverse event, considered by an investigator who is a qualified physician to be related to Merck product that is brought to the attention of the investigator at any time outside of the time period specified in the previous paragraph also must be reported immediately to the Sponsor-Investigator and to Merck.

SAE reports and any other relevant safety information are to be forwarded to the Merck Global Safety [contact]

The Sponsor-Investigator will report significant new safety information associated with use of drugs in this trial (including serious, unexpected, suspected adverse reactions) to FDA in accordance with regulations under 21 CFR 312.32. Additionally investigators will submit a copy of these reports to Merck & Co., Inc. (Attn: Worldwide Product Safety; [contact]) at the time of submission to FDA.

All subjects with serious adverse events must be followed up for outcome.

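### Late immune-related events are not actively sought beyond about 30 days after treatment, although the protocol says they can arise months after the last pembrolizumab dose

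*Combined protocol and SAP*

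**What the plan says.** Safety is a primary objective. Section 3.1.1 reads "To assess the safety and tolerability of the combination of Pembrolizumab and Doxorubicin" in advanced soft tissue sarcoma, with the hypothesis that toxicity resembles that of the two drugs given singly.

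On timing, section 5.2.1.2 says immune-related events "may occur shortly after the first dose or several months after the last dose of pembrolizumab treatment".

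The collection rules are shorter:

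- **All adverse events (7.2):** "All adverse events will be recorded from the time the consent form is signed through 30 days following cessation of treatment". Section 5.6 repeats the 30 days.
- **Last safety visit (7.1.5.3.1, Safety Follow-Up Visit):** "approximately 30 days after the last dose of trial treatment or before the initiation of a new anti-cancer treatment, whichever comes first". Section 7.1.1.5.3 requires this visit to come before any new therapy begun within the 30 days.
- **Serious events regardless of cause (7.2.3.1):** "through 30 days following cessation of treatment, or the initiation of new anti-cancer therapy, whichever is earlier".
- **Serious events outside that window (7.2.3.1):** reportable if considered related to pembrolizumab and "brought to the attention of the investigator at any time outside of the time period specified in the previous paragraph".
- **After confirmed progression or new therapy (7.1.5.3.1, Survival Follow-up):** patients are "contacted by telephone every 12 weeks to assess for survival status". No adverse-event question is attached.
- **Hospice (5.6, 7.1.4.1, 7.1.5.3.1):** follow-up ends.

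**The concern.** The protocol describes a class of pembrolizumab toxicity that can begin months after the last dose, then stops looking for it after about one month, or sooner if the patient moves to other treatment. What remains is passive: a late event counts only if it is serious, is judged related and comes to the investigator's notice. Passive reports give an incomplete numerator and no defined period at risk, so they do not yield a rate.

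At stake is how complete the toxicity profile reported under objective 3.1.1 will be. A table built on the present window describes toxicity during treatment and for about a month afterwards. Readers could take it as the full profile of the combination.

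**Working it through.** **1. The plan's own safety figure.** Section 8.2 says 51 patients allow frequencies, which include toxicities, to be estimated to within 14% with 95% confidence. The half-width at a proportion of 0.5 is 1.96 × √(0.25/n).

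- n = 51: 0.137, which reproduces the stated 14%.
- n = 47 (maximum enrolment, 2.1): 0.143.
- n = 44 (expected enrolment): 0.148.

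The mismatch between 51 and 44 or 47 is a separate matter. What matters here is that the figure covers sampling error in the events recorded. It does not allow for events that fall outside the window.

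**2. When active collection ends.** The sections use two starting points for the 30 days.

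- *Last dose:* 7.1.5.3.1, Safety Follow-Up Visit.
- *Discontinuation:* 2.5, 7.1.5.3 and the flow chart in 6.1 (with ± 7 days there).

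Take a patient who is discontinued at the visit for the next dose, 21 days after the last one. On the last-dose reading, 30 − 21 = 9 days of collection remain. On the discontinuation reading, collection runs to about day 21 + 30 = 51 after the last dose. New therapy can shorten either.

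**3. Share of the risk period covered.** The protocol's several months is not quantified, so 60 to 120 days is an assumed range. The shares are of time, not of events.

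| Assumed risk window after last dose | Covered to day 30 | Covered to day 51 |
|---|---|---|
| 60 days | 30/60 = 50% | 51/60 = 85% |
| 90 days | 30/90 = 33% | 51/90 = 57% |
| 120 days | 30/120 = 25% | 51/120 = 43% |

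Neither reading reaches 60 days.

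**4. Illustration of scale.** The documents give no rate q for a first immune-related event after the window closes. With 44 independent patients, the expected number is 44q and the chance of at least one is 1 − (1 − q)^44.

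| Assumed q | Expected patients | Chance of at least one |
|---|---|---|
| 2% | 0.9 | 59% |
| 5% | 2.2 | 90% |
| 10% | 4.4 | 99% |

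These are events outside active collection. Some would still be reported as related serious events.

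**5. Whether other provisions fill the gap.** Section 7.1.5.3.1 follows adverse events above grade 1 to resolution, but only those already present, and it stops at new therapy. Section 5.3.1 records concomitant medication beyond 30 days for serious events and events of clinical interest; it does not find new events. Section 7.1.2.1 speaks of recording during follow-up, but 7.2 and 7.1.5.3.1 bound that at 30 days.

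**6. Whether planned contacts could serve.** The first survival call falls 12 × 7 = 84 days after entry to survival follow-up. If entry is at least 6 days after the last dose, that call falls on day 90 or later.

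**The case against.** The strongest reply is that serious late toxicity is not lost. Section 7.2.3.1 makes related serious events reportable without time limit, and Table 6 defines grade 3 partly by hospitalisation being indicated, so many grade 3 or higher immune-related events would qualify. This stands as far as it goes. A reader might infer that late serious events go wholly unreported; the documents do not support that. The gap is in active ascertainment, and so in any usable rate.

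Other stronger readings also fail:

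- **Bias toward looking similar to the single agents.** This depends on the collection window behind the single-agent data, which is not stated. If that was also 30 days, the truncation is common to both. Section 8.2 plans only to estimate toxicity frequencies and sets out no formal comparison.
- **Most of the cohort affected.** The 4.6-month median PFS in 4.2.1 is for doxorubicin alone, and no section gives the share moving to further therapy. Patients with benefit may stay on pembrolizumab for up to 2 years under adverse-event review at each cycle, and 2.4 encourages eligible patients with unconfirmed progression to continue for two more cycles.
- **Only 9 days of collection left.** That holds on one of the two readings of the 30 days.
- **The protocol's longer windows elsewhere.** Contraception runs to 120 days, but it concerns fetal risk. Pregnancy reporting (7.2.2) runs to 90 days after completing the trial, but is itself cut to 30 days after cessation when new therapy starts.

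Finally, late events will often be confounded by next-line therapy, and a telephone answer is not a graded event. Both are fair limits on what longer collection can deliver.

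**Conclusion.** The mismatch is real and lies within the protocol: toxicity is expected up to several months after the last dose, but active collection ends at about 30 days or at new therapy. As written, the trial cannot estimate the frequency of late immune-related events for its primary safety objective.

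The size of the loss is unknown. The time shares in the working rest on an assumed 60 to 120 days, and the event counts on assumed rates of 2% to 10%. Phase I DLT decisions are unaffected, because both descriptions of the DLT period (2.5 and 8.2) cover early combination cycles only. Sample size, alpha and power do not change. This is a cheap improvement to data collection that should be made; it does not undermine the design.

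**What to change.** 1. In 7.2, 7.2.3.1 and both parts of 7.1.5.3.1, keep 30 days for general adverse events. Solicit all serious events and grade 3 or higher immune-related events through at least 90 days after the last pembrolizumab dose, regardless of new anti-cancer therapy.
2. Ask a fixed question on these events at the first 12-week call or, for patients still followed for progression, at disease-status follow-up. If that contact falls before day 90, ask again at the next one.
3. State the safety analysis window in 8.2. Tabulate late events separately before and after the start of new therapy, whose initiation is already reviewed under 7.1.1.5.3.
4. Choose one starting point for the 30 days and use it in 2.5, 6.1, 7.1.5.3, 7.1.5.3.1 and 7.2.

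The cost is protocol wording and one question at contacts already planned, with no added visit. Positive answers will need outside records, a physician's causality assessment (Table 6) and, for serious events, reporting within the existing time limits. Separate tabulation shows where next-line therapy confounds an event but does not settle attribution. Patients entering hospice will still be missed.
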